4.3. Demographics and baseline characteristics

Demographic data and other baseline characteristics will be summarized for Safety, FAS, PP and PSPC population by treatment group and overall. The following variables will be summarized:

- Age (years) as continuous variable [(date of ICF signature date of birth)/365.25]
- Race/ethnicity (White vs Other).
- Sex (male / female)
- Body weight without shoes [kg] and height without shoes [cm] at screening and baseline
- BMI [kg/m²] calculated as Weight (kg)/[height (m²)] at screening and baseline.

Weight, height and BMI will be shown both for screening and baseline (Day -1) visit.

Disease characteristic will summarize:

- Duration of disease [years]
- Duration of current exacerbation [days]

- Screening and baseline PANSS score as continuous variable (positive subscale, negative subscale, general psychopathology subscale, total score, Marder 5-factor model subscales)
- Screening and baseline PANSS score as category (low <95, high ≥95)
- Screening and baseline CGI-S items as numerical variable
- Baseline BACS T-score as continuous variable for each task and a composite value.

Separate table will present descriptive statistics for ESRS subscales.

A table will present descriptive statistics for vital signs measured during Screening and Baseline (Day -1) visit: blood pressure [mmHg], heart rate [beats per minute], respiratory rate [breaths per minute], body temperature [°C]. Blood pressure and heart rate will be presented for three time points:

- after 3 minutes lying down
- after 3 minutes sitting, immediately upon standing
- after 3 minutes standing.

Physical examination table will combine results from screening and baseline – in case of new abnormalities observed on Day 1, worst case will be presented in table.

The 12-lead ECG results will be summarized for following parameters: heart rate, ECG finding, PR Value, QRS Value, RR Value, QT Value, QTcF Value

Other baseline characteristics will be listed only.

All other screening or day 1 safety assessments will be listed only unless specified differently below.

4.4. Medical history

Current medical conditions are defined as those entries in medical history that are ongoing at the screening visit. Medical histories and current medical conditions will be coded using a MedDRA dictionary (version of MedDRA current at the time of database lock will be used). Medical histories and current medical conditions will be summarized by treatment group and overall for the full analysis set.

4.5. Concomitant medication

Prior and concomitant medications will be classified using the ATC codes contained in Register of Medicinal Products Approved for Marketing on the territory of the Republic of Poland¹. Summary of concomitant medications will be provided as count and frequency for ATC level 2 (therapeutic subgroup) and 4 (chemical subgroup). Listings of prior and concomitant medications will be provided and sorted by site, patient number, name of active substance, and date of last administration (if known).

4.6. Pharmacokinetic endpoints

The concentration of CPL500036 in plasma will be summarized by dose at each scheduled sampling time using descriptive statistics. Individual plasma concentration data versus time will be presented in a data listing. Plasma PK parameters for CPL500036 will be summarized by dose for subjects with extensive and sparse PK separately using descriptive statistics.

02PDF2010

Statistical Analysis Plan Version 2.0 – 06 Nov 2024

¹ https://rejestrymedyczne.ezdrowie.gov.pl/rpl/search/public

The concentration-time data will be summarized descriptively in tabular and graphical formats (linear and log scales). The PK parameter data will be listed and summarized descriptively in tabular format.

Analyses will be performed for PS and PSPC populations.

The following pharmacokinetic parameters will be estimated if data permits: C_{max} , $AUC_{(0-inf)}$, $AUC_{(0-24h)}$, t_{max} , CL/F, Vz/F, C_{trough} , K_{el} and $t_{1/2}$ for CPL500036. They will be computed using non-compartmental modelling approach using actual sampling times. If multiple peaks occur, the highest post-dose concentration will be reported as C_{max} . In the case that multiple peaks are of equal magnitude, the earliest t_{max} will be reported. The pharmacokinetic parameters will be derived individually for each subject (and day of study if applicable).

All individual pharmacokinetic parameters i.e.: will be presented in listings and analyzed with descriptive summary statistics including arithmetic mean, geometric mean, median, standard deviation (SD), coefficient of variation (CV), minimum and maximum.

Plasma concentration/time curves will be presented in linear and semi-logarithmic scale. Curves will be presented separately for extensive and sparse sampling for:

- individual subjects (including additional semi-logarithmic scale plot showing points used for Kel calculation),
- means for all CPL500036 doses separately for Days 1 and 7,
- means for all days (Days 1 and 7) of study separately for each CPL500036 dose,
- overlapping individual curves (with mean curve in different color) for each CPL500036 dose and for each day of study (Days 1 and 7).

For the individual subject concentration-time graphs, the drug concentrations should be plotted against time using the actual sampling times. For the mean concentration-time graphs the drug concentrations should be plotted using the nominal sampling times.

Additional plasma concentration/time box plots with individual points will be presented for extensive sampling (Days 1 to 7 and Day 28) and sparse sampling (Days 1, 7, and 28) for:

- pre-dose,
- 2 h after administration.

Missing drug concentration data (no value) will be omitted from PK calculations. Drug concentration data below LLOQ will be treated in pharmacokinetic analysis as follows:

- 1. If the concentration below LLOQ is recorded after the last measurable concentration in the dosing interval, then it is omitted from calculations.
- 2. In other cases the concentration below LLOQ concentration value is set to zero.
- 3. If an entire concentration-time profile below LLOQ, the profile will be excluded from the PK analysis.
- 4. A profile of patient with very low concentrations will be excluded from the PK analysis. A profile is considered to have very low concentrations if the $AUC_{(0-24h)}$ for that day is less than 5% of the geometric mean $AUC_{(0-24h)}$, which should be calculated without inclusion of data from the patient.

4.7. Efficacy endpoints

4.7.1. Primary efficacy endpoint

The main analysis will be based on FAS population with supportive analyses using PP population data and imputed FAS population as sensitivity analysis.

For the primary efficacy analysis, change from baseline in the PANSS positive subscale score to week 4 of treatment phase will be analyzed using a mixed model for repeated measures (MRMM), with treatment (placebo, 20 mg, 40 mg), timepoint (all measurements throughout the study will be taken into account: day 1, week 1, week 2, week 3, week 4) and clinical site as fixed effects and baseline score as a continuous covariate. If there will be many clinical sites with few subjects, they can be pooled into bigger groups so the minimum of subjects per grouping will be at least five. Subject will be treated as a random effect, with an unstructured covariance structure to account for the correlation among repeated measurements. If the model does not converge, another covariance structure, (e.g., AR(1), CS, etc.) will be explored. Missing data will be assumed to be missing at random. The R formula which will be used for such analysis:

mmrm(CHANGE ~ TREATMENT * TIMEPOINT + SITE + BASELINE + us(VISIT|ID) using mmrm() function from mmrm library.

Pearson residuals will be used to identifying outlying observations and the appropriateness of the covariance structure. Normalized or scaled residuals will be used to check for normality and will be assessed graphically. Residuals from the primary model will be plotted against the predicted values and a quantile-quantile (QQ)-plot of the residuals versus the expected quantiles of the standard normal distribution will be presented.

The statistical model will allow for comparison of efficacy between placebo and 20 mg, 40 mg, of CPL500036 at each of the timepoint. In order to compare each concentration of CPL500036 to placebo, LS means, their 90% CI, and p values will be calculated using emmeans (Estimated Marginal Means, aka Least-Squares Means) function of emmeans library.

As the null hypothesis is that there are no differences in the primary endpoint between either dose group compared to placebo at week 4, versus the alternative hypothesis, that at least 1 dose group is significantly different, using a 2-sided 10% significance level, no adjustment for multiplicity will be performed for comparisons of each concentration of CPL500036 to placebo at week 4.

Moreover, change from baseline in PANSS positive subscale score at week 1, 2 and 3 will be analyzed on basis of LS-means calculated by MRMM model used in primary endpoint analysis without adjustment for multiplicity.

A sensitivity analysis will be conducted for FAS population whereby missing data is imputed using multiple imputation. Based on that approach, rather than replacing missing values with a single value, we use the distribution of the observed data/variables to estimate multiple possible values for the data points. This allows us to account for the uncertainty around the true value and obtain approximately unbiased estimates. Multiple imputation will be performed using *rbmi* library using a pre-specified seed for random number generator (see section 4.1.5).

The statistical model will allow for comparison of efficacy between placebo and 20 mg, 40 mg of CPL500036.

Descriptive statistics for change from baseline in PANSS positive subscale score at week 4 will be presented by site and by rater as a part of sensitivity analysis.

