10.3. Primary Efficacy Analysis

The null hypothesis is that there is no difference in the primary endpoint between either dose group compared to placebo, versus the alternative hypothesis, that at least 1 dose group is significantly different, using a 2-sided 10% significance level. The primary endpoint will be analysed using a mixed effect repeated measures model (MRMM), with treatment, timepoint, clinical site and interaction between treatment and timepoint as fixed effects and baseline score as a covariate. If there will be many clinical sites with few subjects, they can be pooled into bigger groups. Subject will be treated as a random effect, with an unstructured covariance structure to account for the correlation among repeated measurements. If the model does not converge, another covariance structure, (e.g., AR(1), CS, etc.) will be explored. Missing data will be assumed to be missing at random. A sensitivity analysis will be conducted whereby missing data is imputed using multiple imputation. The primary analysis will compare each dose group with placebo based on estimated marginal means (aka least square means, LS-means) from the model.

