2.4. Sample size

This proof-of-concept study is powered to rule out an effect size of 0.5 or greater for the primary endpoint. With 50 patients per group, the study has 80% power to detect an effect size of 0.5 or greater for 1 of the 2 dose groups, compared to placebo, given a 2-sample t-test, and a 2-sided 10% significance level. Each dose will be compared to placebo, without adjustment for multiplicity so the type-I error will be slightly inflated, however, as this is a proof-of-concept study, the slight inflation is acceptable. Assuming an approximately 10% of patients may drop out, approximately 165 patients will be randomized (55 patients per group).

3. General aspects of the statistical analysis

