4.7.2. Secondary efficacy endpoint

All secondary endpoints will be analyzed without adjustment for multiplicity. The secondary endpoints, which are continuous:

- Change from baseline in PANSS positive subscale at Week 1, 2 and 3 [Time Frame: Weeks 1, 2, and 3].
- Change from baseline in PANSS Total Score at Weeks 1, 2, 3, 4 [Time Frame: Weeks 1, 2, 3, and 4].
- Change from Baseline in PANSS Subscales Using the Marder 5-factor Model at Weeks 1, 2, 3, and 4 [Time Frame: Weeks 1, 2, 3, and 4].
- Change from Baseline in PANSS Negative Subscales at Weeks 1, 2, 3 and 4 [Time Frame: Weeks 1, 2, 3, 4].
- Change from Baseline in PANSS general psychopathology Subscale at Weeks 1, 2, 3 and 4 [Time Frame: Weeks 1, 2, 3, 4].
- Change from Baseline in Clinical Global Impression Severity (CGI-S) Score at Weeks
 1, 2, 3, and 4 [Time Frame: Weeks 1, 2, 3, 4].
- Change from Baseline in Brief Assessment of Cognition in Schizophrenia (BACS)
 Score at Weeks 2 and 4 [Time Frame: Weeks 2 and 4].

will be analyzed using the same approach as described for the primary endpoint using MMRM. Change from baseline in PANSS positive subscale at Week 1, 2 and 3 will be analyzed using primary endpoint MMRM model coefficients to calculate LS means for placebo vs treatment arms comparisons.

Missing data will be assumed to be missing at random. At each timepoint, the LS-means will be reported (by treatment group and for the treatment difference for each dose group, compared to placebo).

The secondary endpoints which are binary (i.e., responder/non-responder):

- Percentage of Clinical Responders Based on the PANSS Total Score. A clinical responder is defined as a ≥ 30% decrease from baseline, [Time Frame: Weeks 1, 2, 3, 4].
- Clinical Global Impression Scale Improvement (CGI-I) Score at Weeks 1, 2, 3, 4 [Time Frame: Weeks 1, 2, 3, 4].
- Percentage of Responders Based on CGI-I Ratings Score at weeks 1, 2, 3, 4. A responder is defined as a rating of 'much improved' or 'very much improved'. [Time Frame: Weeks 1, 2, 3, 4].

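### The primary MMRM fits one baseline slope to every visit, including Day 1 two hours after the first dose, which usually weakens the baseline adjustment at Week 4; a baseline-by-timepoint term recovers the lost precision at almost no cost

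*SAP*

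**What the plan says.** SAP 4.7.1 gives the primary model as "mmrm(CHANGE ~ TREATMENT * TIMEPOINT + SITE + BASELINE + us(VISIT|ID"). BASELINE appears once, with no interaction. The timepoint factor covers five visits: "all measurements throughout the study will be taken into account: day 1, week 1, week 2, week 3, week 4". The covariance is unstructured, with simpler structures as a fallback if the fit does not converge.

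Protocol 10.3 agrees: it lists "interaction between treatment and timepoint as fixed effects and baseline score as a covariate". The synopsis also lists baseline only as a covariate, although it names a different interaction (site by timepoint).

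SAP 4.1.1 takes the PANSS baseline from Day -1. Protocol 8.5.1 and 9.4 place the Day 1 PANSS about 2 hours after the first dose.

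Under SAP 4.7.2 the continuous secondary endpoints "will be analyzed using the same approach as described for the primary endpoint using MMRM".

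SAP 2.4 sizes the trial on an unadjusted comparison, "given a 2-sample t-test, and a 2-sided 10% significance level".

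**The concern.** The slope of change on baseline at a visit equals r × (SD at visit / SD at baseline) − 1, where r is the correlation of that visit's score with baseline. Soon after baseline, r is high and the slope is near zero. By Week 4, r has usually fallen and the slope is more negative. A single coefficient cannot fit both.

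Generalized least squares does not average the visits equally. It favours the visit with the smallest residual variance, normally Day 1. The Week 4 contrast is then pulled toward a plain comparison of change scores.

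At stake are precision already paid for and how far the Week 4 estimate moves when the arms differ by chance at baseline. The amount of adjustment also comes to depend on the covariance structure, so moving to a fallback structure would change it.

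**Working it through.** **Inputs from the documents.** Two-sided alpha 0.10, unadjusted for multiplicity ("using a 2-sided 10% significance level, no adjustment for multiplicity will be performed"); sizing basis "With 50 patients per group, the study has 80% power to detect an effect size of 0.5 or greater"; 55 randomized per group ("Assuming an approximately 10% of patients may drop out, approximately 165 patients will be randomized (55 patients per group"). The documents give no SD, visit correlation or baseline slope, so those below are assumptions.

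**1. The plan's own figure.** Noncentrality = 0.5 × √(50/2) = 2.5 on 98 df gives power 79.9% (normal approximation 80.4%). This reproduces the stated 80%. 50/0.90 = 55.6, against 55 randomized, which is close enough.

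**2. Algebra (complete data).** Week 4 estimate = difference in change − β × difference in baseline. The common slope is β = 1′Wb / 1′W1, where b holds the true visit slopes and W is the inverse residual covariance of the five visits. Relative to visit-specific slopes, the Week 4 residual variance rises by (b₄ − β)² × Var(baseline), where b₄ is the Week 4 slope.

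**3. Illustrative case.** Baseline SD 5. Successive-visit correlations are 0.90 (baseline to Day 1), 0.80, then 0.85 three times, multiplied along the chain for longer gaps.

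| Visit | SD | r with baseline | slope | residual variance | weight in β |
|---|---|---|---|---|---|
| Day 1 | 5.0 | 0.900 | −0.100 | 4.75 | 0.903 |
| Week 1 | 5.2 | 0.720 | −0.251 | 13.02 | 0.030 |
| Week 2 | 5.5 | 0.612 | −0.327 | 18.92 | 0.010 |
| Week 3 | 5.8 | 0.520 | −0.397 | 24.54 | 0.002 |
| Week 4 | 6.0 | 0.442 | −0.469 | 28.96 | 0.056 |

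- The weighted sum gives β = −0.128, against a Week 4 slope of −0.469.
- Excess variance = (0.469 − 0.128)² × 25 ≈ 2.92. Ratio = (28.96 + 2.92)/28.96 = 1.10.
- Variance of Week 4 change = 25 + 36 − 2 × 0.442 × 30 = 34.47 (SD 5.87). An effect of 0.5 SD is 2.94 points.
- Standardized effect: 2.94/√31.88 = 0.520 with the SAP model and 2.94/√28.96 = 0.545 with visit-specific slopes. Power at 50 per group is **82.6% against 85.6%**.
- One standard error of baseline imbalance is 5 × √(2/50) = 1.0 point, which shifts the SAP estimate by about 0.34 point.
- Under homogeneous compound symmetry the weights are equal and β becomes −1.544/5 = −0.31. A convergence failure would thus change the adjustment.

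**4. Sixty assumed patterns** (baseline SD 3.5–5, Week 4 SD 4.5–6, Day 1 correlation 0.80–0.97, Week 4 correlation 0.29–0.64).

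- Day 1 weight: 0.69–1.08 when the Day 1 correlation is at least 0.90; 0.52–1.14 when it is 0.80.
- Common slope: 0.00 to −0.19 (true Week 4 slope +0.09 to −0.68) when the Day 1 correlation is at least 0.90; −0.18 to −0.33 (true −0.10 to −0.71) when it is 0.80.
- Variance increase at Week 4: 0–5% in most patterns where SD widens from 3.5 to 6 (6% at most); 1–15% for SD 4 to 5.5; 2–23% for SD 5 to 6; 6–40% for constant SD.
- Power: 79.7–88.9% with the SAP model, 79.9–92.6% with the interaction; loss 0 to 9.7 points.
- Shift for a one-standard-error imbalance: 0.02–0.54 point, against a target effect of 1.9–3.3 points.

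**5. Simulation check** (165 patients, 10% monotone dropout, no site term, 500 replicates per setting).

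| Pattern | Model | Rejection under null | Power | Shift per point of imbalance (null; effect) |
|---|---|---|---|---|
| Step 3 case | SAP | 14% | 82.2% | −0.45; −0.34 |
| Step 3 case | interaction | 13% | 85.2% | −0.11; +0.02 |
| SD 4.5 throughout, Day 1 r 0.97 | SAP | 11% | 82.8% | −0.53; −0.47 |
| SD 4.5 throughout, Day 1 r 0.97 | interaction | 10% | 91.4% | −0.04; +0.01 |

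Both models centred on the true effect. Monte Carlo error on the null rates is about 1.4 points. The first pattern ran high in both models, so only the comparison between models is informative, and there they are alike.

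**The case against.** The strongest reply is that the size rests on quantities the documents do not supply. Day 1 may track baseline less closely than 0.9: Day 0 lies between the two ratings, the Day 1 rating follows a drug whose commonest Phase I adverse events were drowsiness and somnolence, and PANSS entry thresholds at Day -1 invite regression to the mean. At a Day 1 correlation of 0.80 with constant SD, about half the adjustment survives. If entry criteria narrow the baseline SD and the Week 4 SD widens, little or nothing is lost. All of this stands, and it is why the range starts at zero.

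It also stands that the model is prespecified and valid, that Protocol 10.3 and the SAP agree on it, and that stratifying on baseline total PANSS at 95 (SAP 2.3.2) limits imbalance, though not fully on the positive subscale.

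The mechanism does not reach every secondary endpoint. CGI-S is first rated after baseline on Day 7 (Protocol 8.5.2) and BACS on Day 14 (Protocol 8.5.4). Without Day 1, the variance increase under similar assumptions is at most about 8%, and about 2% with only Weeks 2 and 4.

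None of this favours keeping the single slope. In every pattern checked, visit-specific slopes did as well or better.

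**Conclusion.** The point holds as one of efficiency. A single slope across Day 1 and Weeks 1–4 usually weakens the Week 4 baseline adjustment, often strongly if Day 1 correlates about 0.9 or more with baseline. Under the assumed ranges the Week 4 variance is 0% to about 40% higher than it need be, commonly about 2–20%. The power cost is 0 to about 10 points, about 3 in the illustrative case.

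A reader might infer three stronger things that the documents do not support:

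- **That the adjustment all but vanishes.** This depends on unstated SDs and correlations.
- **That the primary estimate is biased.** It is unbiased over randomizations. The shift is conditional on the imbalance that happens to occur, and it is the same loss of precision seen another way.
- **That the trial is underpowered.** SAP 2.4 assumed no baseline adjustment, so about 80% is kept (79.7% at the lowest). What is lost is power above that.

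**What to change.** Before unblinding, change the SAP 4.7.1 formula to `CHANGE ~ TREATMENT*TIMEPOINT + BASELINE*TIMEPOINT + SITE + us(VISIT|ID)`. State the same term in Protocol 10.3 and the synopsis, in the `rbmi` multiple-imputation model, and in the secondary PANSS models (total, negative, general and Marder factors). It may be used for CGI-S and BACS for consistency, but the gain there is small.

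The cost is four extra parameters in each PANSS model and no new data. Dropping Day 1 from the model instead would recover only part of the loss. In patterns checked for this alternative, the variance was still 4–6% higher than with visit-specific slopes.

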4.7.2. Secondary efficacy endpoint

All secondary endpoints will be analyzed without adjustment for multiplicity. The secondary endpoints, which are continuous:

- Change from baseline in PANSS positive subscale at Week 1, 2 and 3 [Time Frame: Weeks 1, 2, and 3].
- Change from baseline in PANSS Total Score at Weeks 1, 2, 3, 4 [Time Frame: Weeks 1, 2, 3, and 4].
- Change from Baseline in PANSS Subscales Using the Marder 5-factor Model at Weeks 1, 2, 3, and 4 [Time Frame: Weeks 1, 2, 3, and 4].
- Change from Baseline in PANSS Negative Subscales at Weeks 1, 2, 3 and 4 [Time Frame: Weeks 1, 2, 3, 4].
- Change from Baseline in PANSS general psychopathology Subscale at Weeks 1, 2, 3 and 4 [Time Frame: Weeks 1, 2, 3, 4].
- Change from Baseline in Clinical Global Impression Severity (CGI-S) Score at Weeks
 1, 2, 3, and 4 [Time Frame: Weeks 1, 2, 3, 4].
- Change from Baseline in Brief Assessment of Cognition in Schizophrenia (BACS)
 Score at Weeks 2 and 4 [Time Frame: Weeks 2 and 4].

will be analyzed using the same approach as described for the primary endpoint using MMRM. Change from baseline in PANSS positive subscale at Week 1, 2 and 3 will be analyzed using primary endpoint MMRM model coefficients to calculate LS means for placebo vs treatment arms comparisons.

Missing data will be assumed to be missing at random. At each timepoint, the LS-means will be reported (by treatment group and for the treatment difference for each dose group, compared to placebo).

The secondary endpoints which are binary (i.e., responder/non-responder):

- Percentage of Clinical Responders Based on the PANSS Total Score. A clinical responder is defined as a ≥ 30% decrease from baseline, [Time Frame: Weeks 1, 2, 3, 4].
- Clinical Global Impression Scale Improvement (CGI-I) Score at Weeks 1, 2, 3, 4 [Time Frame: Weeks 1, 2, 3, 4].
- Percentage of Responders Based on CGI-I Ratings Score at weeks 1, 2, 3, 4. A responder is defined as a rating of 'much improved' or 'very much improved'. [Time Frame: Weeks 1, 2, 3, 4].

will be analyzed at each timepoint using proportion of subjects who meets the criteria together with confidence intervals, difference from placebo with confidence interval and p value for comparison vs. placebo calculated using a 2-sided 10% significance level proportion test. Logistic regression model will be prepared to explain achievement of response at any time with following factors: treatment (placebo will be the reference value), baseline PANSS Total Score and site as a covariate. If there will be many clinical sites with few subjects, they can be pooled into bigger groups or countries.

In sensitivity analysis for continuous endpoints, similarly to primary endpoint multiple imputation will be used. Binary endpoints analysis will be performed based on non-responder imputation.

